# 6.1.1.2 Phase IIa part:

The regimen applied in Phase IIa will be that with occurrence of a DLT at most in one patient out of 6 patients in the Phase I part and upon final recommendation of the ISC that will prevail. However, should unexpected toxicities or increased numbers of DLTs in an expanded number of patients occur, de-escalation dose levels will also apply in the Phase II part of the study.

#### 6.1.2 Administration of the IMPs

Patients will be receiving intratumoral (IT) injections of Pexa-Vec in combination with nivolumab intravenous (IV) infusions.

[figure not shown]

Figure 1: IMP administration scheme

# 6.1.2.1 Administration of Pexa-Vec

IT Pexa-Vec injections will be performed on D1, D15 and D29. Additional Pexa-Vec boosts may be performed from Week 12 after discussion on a case by case basis between the investigator and Transgene.

Unless contraindicated, all patients will be pre-medicated with acetaminophen (paracetamol), ibuprofen and esomeprazole on each Pexa-Vec treatment day according to the following scheme:

- acetaminophene 1000 mg at 2 hours pre-injection, 6 hours, 14 hours and 22 hours post-injection,
- ibuprofen 400 mg at 2 hours, 10 hours and 18 hours post-injection,
- esomeprazole 40mg, or equivalent.

In case of contra-indication to the prescription of ibuprofen, due to underlying advanced cirrhosis, the investigator may alternatively use the following regimen based on acetaminophen (paracetamol) or equivalent antipyretics, (unless contraindicated):

- 500-1000 mg at 2 hours pre-infusion/injection,
- 500–1000 mg at 4 hours post-procedure,
- 500–1000 mg every 6 hours thereafter, as needed (the total acetaminophen dose should be carefully assessed to avoid cumulative toxicity).

Any treatment may be continued if deemed necessary.

Fevers may be associated with onset of rigors. Meperidine or equivalent may be used for severe rigors.

Unless contra-indicated, patients should also be pre-hydrated with approximately 1 L of solute-containing fluids IV or orally within 12 hours of treatment initiation. In addition, during the post-treatment observation period, patients should receive IV solute-containing fluids or other appropriate treatment as needed for blood pressure support.

Pexa-Vec will be injected into 1 to 5 intrahepatic tumors by a qualified and trained Interventional Radiologist or other trained physician using imaging-guidance (ultrasound and/or CT). As many as possible viable, safely injectable tumors ≥1 cm LD must be treated with a maximum of 5 tumors treated on a given treatment day. Different tumors may be treated on consecutive treatment sessions.

Patients will be monitored closely (e.g., vital signs and clinical observation) the night prior and for 24 hours after the first Pexa-Vec injection as described in the study flow chart (Appendix 1). Hence, hospital admission is required for the first administration of Pexa-Vec. Patients will be monitored the night prior and for at least 8 hours following subsequent Pexa-Vec injections. Longer hospitalization for second, third and additional (boost) administrations of Pexa-Vec is permitted based on Investigator decision.

Pexa-Vec is to be administered after nivolumab on Days 15 and  $29 \pm 1$  day.

### 6.1.2.2 Administration of nivolumab

Nivolumab will be given from D15, by IV route every 2 weeks until progression or unacceptable toxicity. Owing to the possible biphasic evolution of tumor burden often seen with immunotherapeutic products, patients may be treated beyond first evidence of radiologic progression, under specified conditions, as such:

- 1. Patients with a consecutive evidence of radiologic progression and who do not benefit clinically from nivolumab treatment, as assessed by the investigator, should discontinue nivolumab treatment and be treated with another systemic therapy, e.g. sorafenib.
- 2. Patients with a consecutive evidence of radiologic progression and who do benefit clinically from nivolumab treatment could continue nivolumab treatment upon decision of the investigator and after discussion with Transgene Medical Monitor. Clinical benefit is defined as:
  - a. Maintenance of general status
  - b. Absence of disease-related symptoms
  - c. Stability of hepatic function,
- 3. Patients without evidence of progression at a consecutive radiologic assessment with maintenance of clinical benefit are deemed pseudo-progressors and could continue nivolumab treatment.

Nivolumab infusion must not be administered as an intravenous push or bolus injection. Use an infusion set and an in-line, sterile, non-pyrogenic, low protein binding filter (pore size of 0.2  $\mu$ m to 1.2  $\mu$ m). Nivolumab infusion is compatible with PVC and polyolefin containers, glass bottles, PVC infusion sets and in-line filters with polyethersulfone membranes with pore sizes of 0.2  $\mu$ m to 1.2  $\mu$ m.

Patients should be administered nivolumab 240mg as an in intravenous infusion over 60 minutes every 2 weeks ( $\pm$  1 day for cycles 1 to 3 and  $\pm$  3 days for subsequent cycles). For the first infusion, the patient's vital signs (heart rate, respiratory rate, blood pressures, and temperature) should be determined within 60 minutes before, during (every 15 [ $\pm$ 5] minutes), and 30 ( $\pm$ 10) minutes after the infusion. For subsequent infusions, vital signs will be collected within 60 minutes before infusion. Patients will be informed about the possibility of delayed post-infusion symptoms and instructed to contact their study physician if they develop acute symptoms.

Nivolumab will be administered prior to Pexa-Vec on Days 15 and  $29 \pm 1$  day. Owing to the perception by the investigator of the safety of the administration of the two treatments for a peculiar patient or for logistical reasons, the investigator could distribute the treatment administrations over two consecutive days.

# 6.1.3 Duration of treatment and observation period

The expected treatment duration of Phase I and Phase IIa patients depends on the occurrence of unacceptable toxicity events or progression, or on the decision to continue treatment beyond progression, under protocol-specified conditions.

The expected study duration for Phase I and Phase IIa patients depends on CT or MRI scans for efficacy assessment that will be performed every 6 weeks from start of treatment until documented progression or discontinuation of treatment beyond progression or for a period of 12 months after start of study treatment, whichever occurs first.

Beyond 12 months of treatment, the evaluations will be performed every 12 weeks until documented progression or discontinuation of treatment beyond progression. If study treatments are stopped before documented radiological progression, PFS visits will be performed every 6 weeks to continue radiological assessment until documented progression.

# 6.2 Recommended Phase II dose (RP2D)

In the Phase I part, all patients will be monitored up to D29 for the occurrence of DLTs that defines the DLT period. The RP2D is defined as the maximum dose level (1 or -1) at which a DLT attributable to the IMPs is observed at most in one patient out of 6 patients in the DLT period and upon final recommendation of the ISC that will prevail.

The **DLTs**, applicable for the Phase I part of the study, are defined as such:

- 1. All Grade 3-4 non-hematologic toxicity that represents a 2-grade increase over baseline, excluding:
  - Untreated or inadequately treated nausea, vomiting and diarrhea,
  - Untreated or inadequately treated fever > 40.0°C lasting less than 24 hours (Grade 3); only fever > 40.0°C lasting more than 24 hours (Grade 4) qualifies for DLT,
  - Alopecia,
  - Grade 3 fatigue that returns to grade 2 or less within 7 days,
  - Grade 3 laboratory/metabolic abnormalities, other than ALT or AST, that are not considered clinically significant and that return to grade 2 or less within 72 hours.
- 2. Any Grade ≥ 3 treatment-related acute immune-related AE involving major organs, such as: immune-related pneumonitis, colitis, nephritis, hepatitis, endocrinopathies, immune-related rash and other rare but severe immune-related reactions.
- 3. Grade  $\geq$  3 injection site reaction.
- 4. AST or ALT  $\geq$  10xULN, even if asymptomatic, unless it is related to a definite progression of liver metastases or another clearly identifiable etiology; doubling of AST or ALT that is concurrent with a doubling of the total bilirubin.
- 5. Any toxicity at least possibly related to study therapy that results in a delay in treatment of 2 or more weeks.
- 6. Hematological:
  - Grade ≥ 3 or ≥ 2-grade increase over baseline of neutropenia lasting for more than 7 days.
  - Neutropenic fever.
  - Grade 4 thrombocytopenia or grade 3 thrombocytopenia with clinically significant bleeding.
- 7. Cardiac: association of the 3 following cardiac abnormalities
  - Left ventricular ejection fraction (LVEF) less than the lower limit of normal (LLN), as
    assessed by echocardiography and symptomatic due to drop in ejection fraction,
    responsive to intervention,
  - Increase of blood troponin T or I above the upper limit of normal (ULN),
  - Any ECG abnormality consistent with a Grade 3 cardiac disorder.

In the Phase IIa part, should unexpected toxicities or increased number of DLTs in an expanded number of patients be seen, the ISC will be consulted to decide upon dose de-escalation that would re-define the RP2D.

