#### Cardiac evaluation:

- Monitoring for cardiac toxicity will include for both phases of the study:
  - Cardiac echography (ECHO) with measurement of left ventricular ejection fraction (LVEF), if necessary, in addition to baseline measurement,
  - Measurement of troponin T or I blood level 3 and 8 days (± 1) after each Pexa-Vec administration,
  - ECG (12 leads), 8 days (± 1) after each Pexa-Vec administration,
  - ECG (12 leads), 3 days (± 1) after each Pexa-Vec administration, in case of detection of a clinically significant increase in troponin blood level,
  - In the Phase I section, measurement of troponin T or I level will be performed at D29 (end of DLT period), then starting from week 8, ECHO, ECG and troponin T or I level will be performed every 4 weeks (i.e. on every second nivolumab infusion) up to the 28-day safety follow-up visit.

Further examination(s) will be performed if deemed necessary by the investigator.

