[figure not shown]
In addition, in the phase I part of the study, the following assessments will be performed:

- Cardiac echography (ECHO) with measurement of LVEF
- Measurement of troponin T or I level
- 12-lead ECG.

Patients will be observed in the clinic or hospital for a minimum of 8 hours after IT Pexa-Vec treatment. After injection, the following procedures will be implemented:

- Reporting of AEs (that occurred during or after either drug administration) and concomitant medications
- Vital signs (blood pressure, temperature, heart and respiratory rates) 15 minutes (±5 minutes) after injection completion and then every hour (±15 minutes) for at least 8

hours after Pexa-Vec treatment, after which monitoring will be performed every 6 hours up to 24 hours or patient's release from hospital

Patients will be monitored for troponin T or I blood level 3 and 8 days (± 1) after Pexa-Vec administration.

Patients will undergo an ECG 8 days (± 1) after Pexa-Vec administration.

[figure not shown]
Patients will undergo an ECG 3 days ( $\pm$  1) after Pexa-Vec administration, in case of troponin clinically significant increase.

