# 8.7 Radiographic Status Visits: Week 6 ±2 Days and every 6 weeks ±4 Days

At Week 6, radiographic status will be evaluated and then every 6 weeks  $\pm 4$  days up to the End of Treatment Visit.

Beyond 12 months of treatment, the evaluations will be performed every  $12 \pm 2$  weeks until documented progression or discontinuation of treatment beyond progression. If study treatments are stopped before documented radiological progression, PFS visits will be performed every 6 weeks to continue radiological assessment until documented progression. Patients will complete the following procedures:

- Complete physical examination, including weight, vital signs, and ECOG PS
- Skin and mucosal examination; AEs and concomitant medications reporting
- Blood sample collection for the following testing: hematology, chemistry, coagulation, CRP and thyroid blood tests
- Pregnancy test (urine) for WOCBP (if positive, an ultrasound will be performed to confirm pregnancy)
- Tumor assessment: CT or MRI, according to screening assessment
- Patient contact log update
- Week 6 only:
  - o HBV and HCV viral load

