- Dose-limiting toxicity (DLT): Any of the following treatment-related adverse events (AEs) and is evaluated and reported from Baseline through Day 29 in the Phase I section of the study; grades are referring to NCI CTCAE v. 4.03:
  - 1. All Grade 3-4 non-hematologic toxicity that represent a 2 grade increase over baseline, excluding:
    - Untreated or inadequately treated nausea, vomiting and diarrhea,
    - Untreated or inadequately treated fever > 40.0°C lasting less than 24 hours (Grade 3); only fever > 40.0°C lasting more than 24 hours (Grade 4) qualifies for DLT,
    - Alopecia,
    - Grade 3 fatigue that returns to grade 2 or less within 7 days,
    - Grade 3 laboratory/metabolic abnormalities, other than ALT or AST, that are not considered clinically significant and that return to grade 2 or less within 72 hours.
  - 2. Any Grade ≥ 3 treatment-related acute immune-related AE involving major organs, such as: immune-related pneumonitis, colitis, nephritis, hepatitis, endocrinopathies, immune-related rash and other rare but severe immune-related reactions.
  - 3. Grade  $\geq$  3 injection site reaction.

- 4. AST or ALT  $\geq$  10xULN, even if asymptomatic, unless it is related to a definite progression of liver metastases or another clearly identifiable etiology; doubling of AST or ALT that is concurrent with a doubling of the total bilirubin.
- 5. Any toxicity at least possibly related to study therapy that results in a delay in treatment of 2 or more weeks.
- 6. Hematological:
  - Grade  $\geq 3$  or  $\geq 2$ -grade increase over baseline of neutropenia lasting for more than 7 days.
  - Neutropenic fever.
  - Grade 4 thrombocytopenia or grade 3 thrombocytopenia with clinically significant bleeding.
- 7. Cardiac: association of the 3 following cardiac abnormalities
  - Left ventricular ejection fraction (LVEF) less than the lower limit of normal (LLN), as assessed by echocardiography and symptomatic due to drop in ejection fraction, responsive to intervention,
  - Increase of blood troponin T or I above the upper limit of normal (ULN),
  - Any ECG abnormality consistent with a Grade 3 cardiac disorder.

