## 10.9 Toxicity Management

All patients should have blood drawn for laboratory abnormalities assessment before any administration of IMP. Blood draws prior to IMP administration should be tested in the local laboratory.

Management of patients with a DLT within a given dose-escalation cohort: Patients who experience a DLT within a given cohort will be monitored by the Investigator until resolution and the Investigator will report the occurrence of a DLT without any delay or within 24 hours of knowledge or occurrence of the event to Transgene and Transgene representative.

If a patient death occurs within 28 days of the last Pexa-Vec or nivolumab administration due to a serious and unexpected Adverse Drug Reaction (ADR) that is determined by the Investigator or Transgene Medical Monitor to be possibly or probably related to Pexa-Vec and/or nivolumab, further administration of Pexa-Vec /nivolumab will be suspended for ongoing patients. Additionally, further patient enrolment into the study will be suspended and ISC, Ethics Committees (ECs) and Regulatory Authorities will be notified as regards further study handling.

• Management of Adverse Events (other than the formation of pustules)

Patient Management: in case of grade 3 or 4 adverse events considered as related to Pexa-Vec and/or nivolumab, the Investigator should contact Transgene Medical Monitor regarding the management of the patient and to determine if the next administration of Pexa-Vec or nivolumab should be postponed until resolution within an acceptable timeframe (*i.e.* within 30 days) otherwise the Pexa-Vec and/or nivolumab treatment will be stopped (*i.e.* no subsequent injection or infusion, respectively).

• Overall Management in the event of Pustule Formation

Pustule Management: specific precautions should be applied to patients treated with Pexa-Vec, in whom the occurrence of pustules is observed, to prevent contamination from spread of the virus in the environment:

- The infusion sites and any skin lesions should be covered loosely with a non-occlusive bandage (e.g., gauze) held in place with first-aid tape for at least 1 week after treatment. If a blister forms, bandaging of the infusion sites or skin lesions should be continued either until healed or the scab falls off.

- Non-occlusive bandage should be changed at least every 3 days or every time the bandage becomes wet.
- Infectious wastes should be disposed of according to the Institution or local procedures.

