#### 8.8.1 Adverse Events

#### 8.8.1.1 Definitions

From the date of signature of ICF and up to first IMP administration (i.e. before the patient receives any IMP) only SARs caused by a protocol-required procedure (e.g., related to invasive procedures such as blood sampling) will be collected and reported. AEs, SAEs, or procedure related ARs that occur during this period, and that are considered by the investigator as relevant to the patient condition, will be collected as a current medical history.

After the initiation of either IMP and up to 28 days after the last dose of IMP, all AEs and SAEs will be collected and recorded on the eCRF. SAEs will also be reported to Transgene.

SAEs occurring more than 28 days after the last dose of IMP, and evaluated by the Investigator as related to the IMP will be collected and reported to Transgene indefinitely even after end of study. Only SAEs occurring prior to end of study will be reported in the eCRF.

All AEs will be coded using the Medical Dictionary for Regulatory Activities (MedDRA) central coding dictionary using latest version available. NCI-CTCAE version 4.03, dated June 14, 2010 will be used.

All AEs will be reported on the "Adverse Event" section of eCRF.

Dose-limiting toxicity (DLT) is defined as any of the following treatment-related adverse events (AEs) and occurring during the first 4 weeks (up to D29), in the Phase I part of the study; grades are referring to NCI CTCAE v. 4.03:

- 1. All Grade 3-4 non-hematologic toxicity that represent a 2-grade increase over baseline, excluding:
  - Untreated or inadequately treated nausea, vomiting and diarrhea,
  - Untreated or inadequately treated fever > 40.0°C lasting less than 24 hours (Grade
     3); only fever > 40.0°C lasting more than 24 hours (Grade 4) qualifies for DLT
  - Alopecia,
  - Grade 3 fatigue that returns to grade 2 or less within 7 days.
  - Grade 3 laboratory/metabolic abnormalities, other than ALT or AST, that are not considered clinically significant and that return to grade 2 or less within 72 hours.
- 2. Any Grade ≥ 3 treatment-related acute immune-related AE involving major organs, such as: immune-related pneumonitis, colitis, nephritis, hepatitis, endocrinopathies, immune-related rash and other rare but severe immune-related reactions.

- 3. Grade  $\geq$  3 injection site reaction.

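### The DLT count that sets the Phase II dose stops on D29, the day of the last required combination session, so that session has no counted follow-up; two protocol sections also disagree on how long to wait before the safety committee decides

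*Protocol*

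**What the plan says.** **The window.** Protocol 6.2: "In the Phase I part, all patients will be monitored up to D29 for the occurrence of DLTs that defines the DLT period". The same section defines the recommended dose as the highest level with a DLT in at most one of six patients inside that period, subject to the ISC's recommendation, which takes precedence. Protocol 10.1 says a DLT "is evaluated and reported from Baseline through Day 29 in the Phase I section of the study" and closes the period at the third Pexa-Vec administration, given with the second nivolumab infusion. SAP 8.8.1.1 agrees: "occurring during the first 4 weeks (up to D29), in the Phase I part of the study". Protocol 6.6.2 and SAP 2.3 require all three injections and both infusions for evaluability, unless a DLT occurs first.

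**The checks.** Protocol 8.1 (Cardiac evaluation) marks the same closing day for Phase I: "measurement of troponin T or I level will be performed at D29 (end of DLT period". Protocol 8.6 adds, for Phase I at that visit, "Cardiac echography (ECHO) with measurement of LVEF" and a 12-lead ECG, listed ahead of the post-injection steps. After each injection troponin is due at 3 and 8 days, and "Patients will undergo an ECG 8 days (± 1) after Pexa-Vec administration". The next bloods are at Week 6 (Protocol 8.7): "Blood sample collection for the following testing: hematology, chemistry, coagulation, CRP and thyroid blood tests". Protocol 10.9 places blood draws ahead of dosing: "All patients should have blood drawn for laboratory abnormalities assessment before any administration of IMP".

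**Timing of the decision.** Protocol 3.1.1, in its de-escalation paragraph, describes an interval of a month or more between the last patient's DLT period and the ISC decision on the first dose level. Protocol 14.4 has the ISC meet no later than two weeks after a Phase I cohort is complete. SAP 7.2 triggers the review when six evaluable patients have reached Day 29.

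**The concern.** A 1-of-6 rule protects Phase IIa patients only against events that it counts. Here the session that completes the required exposure, and is only the second co-administration, falls on the closing day. A qualifying cardiac, haematological or injection-site event with onset on D30 or later does not enter the count, however clearly it meets the DLT criteria. Whether it changes the dose then depends on a landmark category or on ISC judgement. Protocol 1.7 itself raises the possibility that the combination increases the risk of myocarditis, and the landmark definitions in Protocol 3.1.1 and 6.1.1.1 do not name cardiac events. If the count passes with no landmark AE and the ISC agrees, Phase IIa accrues at the same dose with no spacing between patients.

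The text also does not say what happens when an event starts by D29 but meets its duration criterion later (neutropenia beyond 7 days, or a treatment delay of 2 weeks or more).

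**Working it through.** **1. Reproduce the schedule.** Injections are on D1, D15 and D29. Third-session checks: 29 + 3 = D32 and 29 + 8 = D37, matching the Appendix 1 flow chart. Week 6 = 1 + 42 = D43.

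**2. Counted follow-up per session** (window end minus session day).

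| Window ends | D1 | D15 | D29 |
|---|---|---|---|
| D29 (current) | 28 days | 14 days | 0 days |
| D43 (Week 6) | 42 days | 28 days | 14 days |

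**3. Routine post-injection checks inside the current window.**
- Troponin D4, D9, D18, D23, D32, D37: 4 of 6 inside, 2 outside.
- ECG D9, D23, D37: 2 of 3 inside, 1 outside.
- Next pre-dose bloods D15, D29, D43: 2 of 3 inside, 1 outside.

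The Phase I echocardiogram, troponin and ECG at the D29 visit are inside the window, but they mainly reflect the first two sessions.

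**4. Duration criteria.** With the SAP 7.7.2 convention (end − start + 1), neutropenia starting on D23 has lasted 29 − 23 + 1 = 7 days at D29, so it cannot yet exceed 7 days. For third-session toxicity the next planned dose is D43. A 2-week delay could first be established on D43 + 14 = D57.

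**5. What the ISC can see.** Patient 2 starts after patient 1's D29, then there are 14 days between patients (Protocol 3.1.1). The earliest starts are calendar days 1, 29, 43, 57, 71 and 85, so patient 6 reaches D29 on day 85 + 28 = 113.

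| ISC review on | Days past own D29, patients 1 to 6 |
|---|---|
| Day 113 (earliest under SAP 7.2) | 84, 56, 42, 28, 14, 0 |
| Day 127 (Protocol 14.4 limit; also patient 6's Week 6) | 98, 70, 56, 42, 28, 14 |
| Day 143 (Protocol 3.1.1, month taken as 30 days) | 114, 86, 72, 58, 44, 30 |

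Patients 1 to 5 have all reached Week 6 by day 113, so only patient 6's D30 to D43 can be unseen.

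**6. The two intervals.** If completion means the last patient's D29, at most 14 days (14.4) and about 30 days or more (3.1.1) cannot both hold. SAP 7.2 names a data trigger, not a meeting date, so it fits either.

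**7. Illustration only.** The documents give no DLT rate for the combination; Protocol 1.4.1.1.2 reports one DLT in a 47-patient study of nivolumab alone. Assume a three-session risk p, with H = −ln(1 − p), and a share s of that hazard falling after the window. Counted risk = 1 − exp(−H(1 − s)), and P(more than 1 of 6) is binomial.

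| p | s = 0 | s = 1/6 | s = 1/3 |
|---|---|---|---|
| 10% | 11.4% | 8.4% | 5.7% |
| 25% | 46.6% | 37.7% | 28.2% |
| 40% | 76.7% | 67.5% | 55.5% |

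Example: p = 25%, s = 1/3 gives H = 0.288, counted risk 17.5%, and P = 28.2%.

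**The case against.** The count is not the only gate. The ISC analyses all Phase I safety results, its view prevails (Protocol 3.1.1, 6.2), no new cohort starts without its advice, and it meets within days of a related severe or serious event that may need a decision, ahead of further enrolment (14.4). One landmark AE triggers de-escalation with no D29 limit, and the landmark categories overlap the hepatic and immune-related DLT criteria. The dose can also be redefined in Phase IIa (6.2). Protocol 3.1.1 gives a rationale: Pexa-Vec events usually settle within days, and the month before the ISC decision is meant to reveal late events. On that view a four-week window with committee override is a reasoned choice.

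All of this stands as a limit on weight. It does not supply a counting rule for non-landmark events after D29, and the late-observation month is the interval that 14.4 appears to contradict.

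Two practical objections also stand. The cardiac DLT needs a symptomatic low ejection fraction, raised troponin and a Grade 3-type ECG finding together. The next scheduled Phase I echocardiogram after D29 is at Week 8, so a later window alone does not complete that criterion. And Phase I recruitment was planned to finish by January 2018 (3.1.3), before the March 2019 protocol version, so a prospective change may come too late.

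A reader might infer that toxicity after D29 goes unmonitored, or that the SAP adds a third conflicting interval. The documents support neither: late events are collected and reviewed, and SAP 7.2 is compatible with both protocol intervals. SAP 7.5 also requires a data review meeting first, which makes a same-day review unlikely.

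**Conclusion.** The point holds as a gap in the pre-specified rule, and it is worth fixing. The last required session has 0 days of counted follow-up beyond its dosing day. The exposed toxicities are mainly cardiac, haematological, injection-site and others outside the landmark categories. For patients 1 to 5 the later data are visible but uncounted; for patient 6, D30 to D43 may be unseen, depending on when the ISC meets. This rests on the earliest permitted stagger; slower accrual only lengthens follow-up for patients 1 to 5.

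The timing disagreement is between Protocol 3.1.1 and 14.4 alone, and depends on reading cohort completion as the last patient's D29, which 14.4 does not define.

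The probabilities show direction, not expected size. They use assumed rates and ignore the landmark trigger and the ISC override, so they should not be read as the chance that the trial adopts a toxic dose. Nor is the one-third case an upper bound. It corresponds to equal risk per session with nothing seen on D29. Protocol 8.1 expects milder reactions at later injections, which would lower the missed share; D1 involves no nivolumab, so combination risk could fall more heavily on D29 and raise it.

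**What to change.** 1. Extend the DLT period and the 1-of-6 rule through the Week 6 pre-dose assessment in Protocol 3.1.1, 6.2 and 10.1 and SAP 7.2 and 8.8.1.1, with matching wording in the synopsis, Protocol 6.6.2 and SAP 6.1. Count an event by onset in that period, even if its duration criterion is met later.
2. Require an echocardiogram if the D32 or D37 troponin or ECG is abnormal. Protocol 8.1 already allows one beyond baseline when needed.
3. Hold the cohort ISC review until patient 6 completes Week 6, and align Protocol 3.1.1, 14.4 and SAP 7.2 on that rule. State whether patient 2's entry stays tied to patient 1's D29.
4. If Phase I is complete, adjudicate recorded events from D29 to Week 6 against the DLT criteria and report that count beside the recommended dose. The listings in SAP 8.8.1.3 already carry onset day, grade, relatedness and a DLT flag.

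**Cost.** No scheduled visit is added; the echocardiogram is conditional. Patient 6's Week 6 is day 127: 127 − 113 = 14 days after the earliest SAP trigger, equal to the 14.4 limit and earlier than day 143 under 3.1.1. The read-out delay is therefore 0 to 14 days. Holding patient 2 to Week 6 as well moves patient 6's Week 6 to day 141, a delay of up to 141 − 113 = 28 days. A patient who leaves between D29 and Week 6 without a DLT may need replacing. If Phase I is over, the cost is one adjudication of existing data.
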